## SYNOPSIS OF THE CLINICAL INVESTIGATION

---

Title: An exploratory investigation of the effects of single use vs. reuse catheters in intermittent catheterization

The overall aim of the investigation is to investigate the effect of repeated reuse of intermittent urinary catheters and to observe the impact of switch from single use to multiple reuse catheters.

Throughout the investigation, the impact of switch from single use to multiple reuse catheters will be observed and compared with respect to health-related quality of life (HR-QoL), satisfaction, perception, and preference in female and male catheter-users, who use clean intermittent catheterization (CIC) for bladder management.

Furthermore, the investigation intends to identify microbial contamination of reused catheters and compare proportions to a control single use catheter.

### Test products

The CP352 investigational device is the CE-marked CLINY reuse catheter (CLINY Self-Catheterization Set) which is a reusable catheter made of 100% silicone rubber to be reused for a maximum of 28 days before disposal.

### Intended use and purpose

The device is to be inserted temporally into the patient's urethra and bladder for urination (see instruction for use in Appendix A). For this investigation the device is to be inserted temporally into the participating subjects' urethra for drainage of the urine bladder.

### Objectives

The objective is to compare health-related quality of life (HR-QoL) when using single use catheters with reuse catheters.

The **primary objective** is to investigate whether the reuse catheter CLINY can impact health-related quality of life in CIC users when compared to single use.

The **secondary objectives** are to evaluate whether the reuse catheter CLINY can impact satisfaction, perception, preference, and microbial contamination when compared to single use.

### Design of the investigation

The investigation is designed as an open-labelled, single-arm investigation including subjects currently using single use catheters.

The cohort will in total consist of 40 CIC users, who must test reusable catheters. Each subject will participate for approximately 4 weeks, including up to 3 site visits and 3 phone visits, overseen by the investigator, or delegate, within the 4-weeks home test period.

### Expected duration of the clinical investigation

The investigation will be conducted from June 2022 through March 2023.

Each subject will undergo screening and baseline visits, which can be performed the same day, followed by a 4-week (28-days test period). When the 28-days test period is completed, a termination visit will be performed.

### Primary, secondary, and exploratory endpoints

Primary endpoint:

- Health-related quality of life (HR-QoL) measured by the intermittent self-catheterization questionnaire, (ISC-Q) index score

Secondary endpoints:

- Adverse events

Exploratory endpoints:

- Intermittent Catheterization Satisfaction (InCaSa) questionnaire score
- Perception questions (evaluated on a 6-point scale)
- Total catheter-associated bacterial count (CFU/mL)
- Number of bacterial-positive catheter samples

## Population and subjects

The clinical investigation will be conducted in a total of 40 subjects male and female CIC users recruited at multiple clinical investigational sites in Denmark. To be included in the investigation, the subjects must comply with the selected criteria described below.

## Inclusion and exclusion criteria:

Inclusion criteria	Exclusion criteria
1. ≥18 years of age and has full legal capacity	1. Participation in any other clinical intervention study during this investigation
2. Signed informed consent form	2. Previous participation in this investigation
3. Use clean intermittent catheterization to the greatest extent possible (at least three times daily) for at least the last 1 month prior to inclusion	3. Any known allergies towards ingredients in the investigational device
4. Ability (assessed by the investigator) and willingness to participate in a 4-week study period with at least three catheterizations a day using the investigational test product	4. Symptoms of UTI at time of inclusion, as judged by the investigator
5. Self-catheterize using a single use hydrophilic coated catheter for at least 1 month prior to inclusion	5. Antibiotic treatment within 2 weeks prior to the Baseline visit (V1)
	6. Pregnancy
	7. Breastfeeding

## 2. Rational/justification for conducting the clinical investigation

In patients with neurogenic or non-neurogenic bladder dysfunction, intermittent catheterization (IC) is a well-accepted tool for bladder management, ensuring patient independence and improved quality of life.

To minimize the risk of urinary tract infections (UTIs), the use of sterile, single use catheters has for many years been the recommended standard of care. However, based on cost and an environmental agenda, a push for reuse catheters has emerged. International associations do not currently endorse catheter reuse due to the lack of standardized cleaning and reuse recommendations and a concern of decreased compliance, unsafe practice and increased risk of UTIs. There is at present a lack of solid evidence with respect to risk of UTIs associated with single use vs. reuse, though one recent metanalysis including > 900 users found single use catheters to be the only catheter associated with reduced UTI rate.

Deciphering the influence of catheter per se is complicated by the highly complex and multifactorial causalities associated with UTIs in IC users, however, a recent study demonstrated significant bacterial contamination on reuse catheters. Also, there was an end-study preference towards single use and increased health-related (HR) QoL, when changed from reuse to single use catheter. These results align well with user concerns, namely, the risk of UTIs and the burden of repeated daily cleaning procedures.

In alignment with these concerns, the aim of the present investigation is to investigate potential user challenges and level of catheter contamination, associated with introducing re-use catheters in a patient population accustomed to single use catheters. Thus, addressing the influence of catheter choice on HR-QoL and treatment satisfaction, the primary aim of this investigation is to analyse single use vs. re-use, using validated IC-specific questionnaires. To better evaluate the risk of potential catheter contamination at time of catheter reuse, the secondary aim is to analyse bacterial colonization after catheter cleaning and storage, just prior to catheterization.

The overall aim of the investigation is to investigate the effect of repeated reuse of intermittent urinary catheters and to observe the impact of switch from single use to multiple reuse catheters.

## 3. Objectives and hypotheses of the clinical investigation

### 3.1. Objectives

The **primary objective** is to investigate whether the reuse catheter CLINY can impact health-related quality of life in CIC users when compared to single use.

The **secondary objectives** are to evaluate whether the reuse catheter, CLINY can impact satisfaction, perception, preference, and microbial contamination when compared to single use.

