### 5.3. Secondary and exploratory endpoints

**Secondary endpoints:**

- Adverse events

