**Exploratory endpoints:**

- Satisfaction of intermittent catheterization measured by the InCaSa questionnaire score
- Perception questions (evaluated on a 6-point scale)
- Total catheter-associated bacterial count (CFU/mL)
- Number of bacterial-positive catheter samples

See Appendix H for endpoints and assessments.

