## **6. Clinical Investigation population**

The clinical investigation will be conducted in 40 subjects enrolled in multiple clinical investigation sites. The enrolment is competitive.

To allow for statistically significant data, a minimum of 20 eligible completed subjects in multiple clinical investigation sites will be adequate for obtaining indications on the effects of repeated reuse of catheters, hence the aim for this investigation is 20-40 completers.

Considering a drop-out rate of 50 %, the total number of subjects to be enrolled must be 40.

Recruitment and discontinuation will be followed very closely, and all replacements evaluated on an ongoing basis depending on both number of discontinued subjects and the time the subjects participated in the investigation. As a minimum sponsor will make a status on the recruitment strategy every month or at least when half of the subjects have been recruited.

The aim is to keep the LPO date. If concerns of high dropout rate recruitment/retention arise and status will be discussed by sponsor.

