## 10. Statistical considerations

### 10.1. Statistical design, method, and analytical procedures

Baseline assessments and endpoints will be reported by descriptive statistics and/or listed. Summaries will be presented by device i.e., IC and re-use catheters and if relevant, by other grouping variables.

Descriptive statistics for continuous variables are presented with N, Mean, SD (standard deviation), Median, Min and Max, where N denotes the number of subjects contributing with non-missing data. For discrete variables, descriptive statistics are presented with N and percentage, where percentage is based on the total number of subjects/observations with non-missing data.

All statistical analysis will be performed with [REDACTED]

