### 10.4. Analysis of the secondary and exploratory endpoints

Adverse events and exploratory endpoints will be reported and evaluated by descriptive statistics.

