### **Following question to the subject, to be completed by PI or delegate:**

- Reason for drop-out (in case of discontinuation prior to 28 test days)
  - Reason not stated by the subject
  - Inconvenient to use
  - I was concerned about getting an infection/UTI
  - It was difficult to handle
  - It was too time consuming to use
  - Lack of discretion
  - It was uncomfortable to use the catheter
  - Other (text)

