## Appendix H: Endpoints and Assessments

Endpoints and assessment		Assessed by	V1 (Baseline)	V2 (Phone Call)	V3 (Phone Call)	V4 (Phone Call)	V5 (Termina- tion)
Primary end-point	Health-related quality of life (HR-QoL) measured by intermittent self-catherization questionnaire, (ISC-Q) index score at Baseline Visit (V1) and at the termination Visit (V5) Appendix A	Subject	X				X
Secondary endpoint	The secondary endpoint will be an evaluation of adverse events from time of signed informed consent and throughout the test period.	Site	X	X	X	X	X
Exploratory endpoints	Satisfaction of intermittent catheterization measured by the InCaSa questionnaire score	Subject	X				X
	Perception questions (evaluated on a 6-point scale)	Subject	X				X
	Total catheter-associated bacterial count (CFU/mL)	Coloplast Laboratory	X				X
	Number of bacterial-positive catheter samples	Coloplast Laboratory	X				X
Assessments	Urine Dipstick for haematuria, leucocytes, and nitrite  (Baseline Visit and Termination Visit the dipstick is performed at site).  (Visit 2, 3 and 4 the dipstick will be performed by subject at home)	Subject/Site	X	X	X	X	X
	Preference (Appendix E)	Subject					X
	Reason for drop out if Termination Visit is performed prior to 28 test days	Site					X

Endpoints and assessment	Assessed by	V1 (Baseline)	V2 (Phone Call)	V3 (Phone Call)	V4 (Phone Call)	V5 (Termina- tion)
Evaluation of catheterization since last visit:  Have the subject used single use catheters since last Baseline Visit	Subject/Site		X	X	X	X
Did the subject follow all cleaning procedures stated in the IFU?						
Average number of daily catheterizations with CLINY the subject completed since last visit						
Average time spent on each catheterization from preparation to storage/disposal (in minutes)						
Visual and microscopic evaluation of the CLINY catheters for defects (defects/no defects)	Coloplast Laboratory					X
Electron microscopy scanning and confocal microscopic evaluation of the catheters surface (defects/no defects)	Coloplast Laboratory					X
Changes in Concomitant medication	Investigator	X	X	X	X	X
For female subjects of childbearing potential: urine pregnancy dipstick	Subject/Site	X

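### Preference is a secondary objective with no endpoint, and its percentage would rest only on subjects who answer at the Termination Visit (V5)

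*Combined protocol and SAP*

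**What the plan says.** Section 3.1, like the synopsis, states that the secondary objectives "are to evaluate whether the reuse catheter, CLINY can impact satisfaction, perception, preference, and microbial contamination when compared to single use".

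The endpoint lists do not follow from this. Section 5.3 gives one secondary endpoint, "Adverse events". Its exploratory list opens with "Satisfaction of intermittent catheterization measured by the InCaSa questionnaire score" and continues with the perception questions, the bacterial count and the number of bacterial-positive samples. Preference is in neither list, nor in Section 5.2. Appendix H places it among the assessments, at V5 only, and Section 7.1 and Table 5 agree. Appendix E makes it a two-way choice between the single use and the reuse catheter.

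On analysis, Section 10.1 describes reporting for baseline assessments and endpoints, and Section 10.4 says "Adverse events and exploratory endpoints will be reported and evaluated by descriptive statistics". For discrete variables Section 10.1 adds that "percentage is based on the total number of subjects/observations with non-missing data". No rule covers a missing preference answer.

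On drop-out, Section 6 says "Considering a drop-out rate of 50 %, the total number of subjects to be enrolled must be 40". Appendix E lists eight reasons for stopping. Six are objections to using the device, for example "It was too time consuming to use"; the other two are an unstated reason and a free-text option.

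On V5 after early stopping, Section 5.1 plans the visit with its full set of assessments, Section 6.3 calls for it when a subject is withdrawn for antibiotic treatment, and Section 10.5 says that discontinued subjects will be asked to complete it.

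**The concern.** Read strictly, a declared secondary objective has no planned analysis, because preference is neither a baseline assessment nor an endpoint. If the general rule of Section 10.1 is applied to it, the denominator is the set of subjects who answered.

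That matters because non-response is unlikely to be random. Someone who gives up CLINY because it is awkward, slow or uncomfortable, and then does not come to V5, leaves no answer. Such a person probably prefers single use. The percentage would then describe those who answered at V5, whereas the objective concerns users switched to reuse. If non-responders do lean to single use, the figure flatters CLINY, and more so as more drop-outs miss V5. Replacement of subjects who stop before day 14 (Sections 6.3 and 10.5) can add to this: the replacement may supply an answer while the replaced subject does not.

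**Working it through.** **The plan's own figure.** 20 completers at 50% drop-out: 20 / (1 − 0.50) = 40, which matches the enrolment stated in Section 6.

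**Inputs.** From the documents: 40 subjects and 50% drop-out, so 20 completers and 20 drop-outs. Assumed for illustration: all 40 used CLINY, every completer answers, 12 of the 20 completers prefer CLINY, and every drop-out prefers single use. The share *s* of drop-outs who complete V5 is not given, so it is varied from 0 to 1. Replacements are ignored.

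**Formulas.** Percentage under Section 10.1 = 12 / (20 + 20*s*). Missing answers *m* = 20(1 − *s*). Lower bound, all missing counted as single use: 12/40. Upper bound, all missing counted as reuse: (12 + *m*)/40.

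| Drop-outs completing V5 | Reported | Bounds over all 40 |
|---|---|---|
| 0% | 12/20 = 60% | 30% to 32/40 = 80% |
| 25% | 12/25 = 48% | 30% to 27/40 = 67.5% |
| 50% | 12/30 = 40% | 30% to 22/40 = 55% |
| 75% | 12/35 = 34% | 30% to 17/40 = 42.5% |
| 100% | 12/40 = 30% | 30% (none missing) |

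Exact (Clopper-Pearson) 95% intervals: 12/20, 36% to 81%; 12/30, 23% to 59%; 12/40, 17% to 47%.

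**Other observed shares, with no drop-out completing V5.** 6/20 = 30% reported, bounds 15% to 65%. 10/20 = 50% reported, bounds 25% to 75%. 14/20 = 70% reported, bounds 35% to 85%.

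**Few missing answers.** If only 10% of the 40 lack an answer and 18 of 36 prefer CLINY, 50% is reported. The bounds are 18/40 = 45% and 22/40 = 55%.

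**Does the analysis set help?** No. Under Section 10.2 the full analysis set needs exposure to a device and one recorded endpoint, so a baseline score keeps a drop-out in the set. The percentage denominator is still the number of answers.

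**The case against.** The strongest reply is that the plan already deals with early stoppers. Section 5.1 gives them V5 in full, preference included, and Section 10.5 repeats the request. This stands, and it confines the problem to those who do not complete V5. It does not remove it: Section 10.5 only asks, and Section 6.3 lets subjects withdraw at any time and expects some to be lost.

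A second reply is that percentages over observed answers, with N shown, are normal in a descriptive study without pass/fail criteria, and that the missing count can be recovered from N. That is fair, but N does not show how far the missing answers could move the result.

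Third, giving no answer is not the same as preferring single use. Appendix E is a list of options, not a set of frequencies, and some withdrawals, such as those for antibiotic treatment, are not the user's rejection of the device. This also stands.

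A reader might infer that drop-outs without an answer can be counted against CLINY from their recorded drop-out reason. The documents do not support that: the reason is itself collected at V5 (Section 7.1, Section 10.5, Appendix H), so a subject who misses V5 has no scheduled record of either item. A reader might also take the contact attempts in Section 6.3 to cover this already. They serve only to verify loss to follow-up, and the same section says withdrawn subjects without adverse events are not followed up.

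**Conclusion.** The gap between objective and endpoints is plain on the documents: preference is the only one of the four secondary objectives with no endpoint. That the non-missing rule governs its percentage is an inference, since it is the only general rule available and the plan does not name preference in Section 10.

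The bias is possible, not established. Its size depends on V5 completion among drop-outs, which the documents do not estimate, and its direction on drop-outs favouring single use, which is plausible from Appendix E but not stated. Under the illustrative assumptions the reported share runs from 60% to 30%, enough to turn a majority for CLINY into a minority. If every drop-out completes V5, no bias arises from this source.

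A reader might conclude that the planned 50% drop-out by itself doubles the reported preference. That is only the extreme case in which no drop-out completes V5 and all of them prefer single use; Section 5.1 plans for the opposite. The point deserves a change because the remedy is cheap and the result answers a declared objective.

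**What to change.** 1. Name preference as an exploratory endpoint in Section 5.3 and Appendix H, and in the synopsis list.
2. In Sections 6.3 and 10.5, state that when V5 is declined or missed the site takes both the preference question and the drop-out reason by phone, either at the contact where V5 is declined or during the attempts made for loss to follow-up.
3. In Section 10.4, report preference over all subjects who used CLINY at least once, replaced subjects included, in three categories: single use, reuse, missing. Give the percentage among observed answers with an exact 95% confidence interval. Add two bounds, counting all missing as single use and then all as reuse.
4. Do not make imputation from the drop-out reason the main estimate. It works in one direction only, and for subjects who miss V5 the reason may be missing too.

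Cost: wording in these sections and a short phone question. The phone question is a small addition to site work, not a step already required. No new visit or subject is needed. The reported range for CLINY becomes wider and possibly less favourable.

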### 3.2. Hypotheses

No formal success criteria are applied in this investigation. The investigation will provide valuable insight into performance and evaluation of effects, impact, and comparison of a switch from single use catheters to reusable catheters.

[figure not shown]
## 4. Investigational device

The investigational device is the CE-marked reusable Self-Catheterization Set, named CLINY. The Set is a Self-Catheterization Set produced by the Japanese company Create Medic co., LTD.

### 4.1. Description of the investigational device

The CLINY Self-Catheterization Set consists of four non-sterile parts:

- A foldable catheter case of polypropylene, silicone rubber (can be folded into a small size)
- A cap of polypropylene, silicone rubber
- A catheter of silicone rubber
- An outer case to carrying with the catheter case

**Figure 1: CLINY Self-Catheterization Set**

The following catheter sizes for female and male will be available in the investigation. See Table 1.

**Table 1: Investigational devices available in the investigation**

	Size	Length	Content
Female	12 FR	165 mm	CLINY Self-Catheterization Set
Male	12 FR	395 mm	CLINY Self-Catheterization Set
Male	14 FR	395 mm	CLINY Self-Catheterization Set

#### **4.3. Identification and traceability of the device**

The investigational device is the CE marked physical test product identified as CLINY Self-Catheterization Set. The investigational product will be used according to the intended use and will be stored safe and controlled at site. The Investigator Site File includes an accountability log for the control of the investigational device.

All the investigational devices are labelled as per regulations and include "Exclusively for clinical investigational use" (Udelukkende til klinisk afprøvning). The devices are also identified with an investigation number, product name/code, and item/Lot number and accounted through a master sponsor accountability log.

Upon EC approval, the investigational devices will be shipped to the Principal Investigator or delegate(s). Additionally, all investigational devices will be accounted for and documented on a site accountability log. All used and unused devices will be returned to Coloplast.

#### **4.4. Intended use of the device in the clinical investigation**

The investigational test product is a Self-Catheterization Set for re-use in 28 days and is only to be used for drainage of the bladder through the urethra. The product is a MDR class 1 device.

#### **4.5. Intended population for the device**

The intended population for this investigational device is males and females who are depending on clean intermittent catheterization for bladder management.

#### **4.6. Handling of the investigational device**

Handling of the CLINY Self-Catheterization Set with reusable catheter is described in detail in the instruction for use (IFU), which is included in all boxes with the investigational device.

See the IFU in Appendix A.

The Principal Investigator and delegate(s) will receive training by the sponsor in handling and correct use of the investigational device. The PI or delegate will train the subject in the correct use of the investigational device according to the IFU.

